# TITLE: A comparison of a Combination of Aspirin and Oral Ketamine (VTS-K formulation) to Oral Ketamine alone in adult patients presenting to the ED with acute musculoskeletal pain: prospective, randomized, open-label, clinical trial.

#### INTRODUCTION

Acute Pain is one of the most frequent chief complaints and the main reason for visiting the Emergency Department (ED). The acute pain in the ED is largely prevalent across the country with recent literature demonstrating that 61-91% of patients are admitted to the ED due to a variety of acute painful syndromes. There is a lack of good options for pain control in such settings.

#### **STUDY OBJECTIVES**

To compare analgesic efficacy and rates of side effects of a proprietary formulation of orally administered aspirin and ketamine (AOK) to a proprietary formulation of Oral Ketamine (OK) (VTS-K formulations) for pain management in adult ED patients presenting to the ED with acute musculoskeletal pain

#### HYPOTHESIS

We hypothesize that the administration of AOK will provide better analgesia at 60 minutes post-administration in comparison to OK in adult patients presenting to the ED with acute musculoskeletal pain. The primary outcome of this trial is the comparative reduction in participant's pain scores at 60 minutes post-medication administration.

### **STUDY DESIGN**

**Subjects:** Patients 18 years of age and older presenting to the ED with acute musculoskeletal painful conditions (traumatic and non-traumatic) with an initial pain score of 5 or more on a standard 11- point (0 to 10) numeric rating scale and requiring oral analgesia as determined by the treating attending physician. Patients' screening and enrollment will be performed by study investigators and research assistants. All patients will be enrolled at various times of the day when study investigators will be available for patient enrollment and an ED pharmacist will be available for medication preparation.

**Eligibility Criteria:** Patients 18 years of age and older presenting to the ED with acute musculoskeletal painful conditions (traumatic and non-traumatic) with an initial pain score of 5 on a standard 11- point (0 to 10) numeric rating scale. Patients will have to be awake, alert, and oriented to person, place, and time, and will be able to demonstrate understanding of the informed consent process and content. Patients also will have to demonstrate ability to verbalize the nature of any adverse effects they might experience as well as to express their pain severity by using the NRS.

**Exclusion Criteria:** Patients with altered mental status, allergy to aspirin and ketamine, pregnant patients, unstable vital signs (systolic blood pressure <90 or>180 mm Hg, pulse rate <50 or >150 beats/min, and respiration

rate <10 or >30 breaths/min), inability to provide consent, consumption of Aspirin or NSAID's within 6 hours of arrival to the ED, active PUD, history of GI Hemorrhage, history of renal and hepatic insufficiency, past medical history of alcohol or drug abuse, or schizophrenia.

**Design:** This is a prospective, randomized, open-label trial comparing analgesic efficacy and safety of AOK and OK in patients presenting to the ED of Maimonides Medical Center with acute musculoskeletal pain. Upon meeting the eligibility criteria, patients will be randomized into one of the two study arms: Group I will receive AOK and Group II will receive OK.

**Data Collection Procedures:** Each patient will be approached by a study investigator for acquisition of written informed consent and Health Insurance Portability and Accountability Act authorization after being evaluated by the treating emergency physician and determined to meet study eligibility criteria. When English will not be the participant's primary language, a language- appropriate consent form will be used and non-investigator, hospital-employed, trained interpreters or licensed telephone interpreter will assist in acquisition of informed consent. Baseline pain score will be determined with an 11-point numeric rating scale (0 to 10), described to the patient as "no pain" being 0 and "the worst pain imaginable" being 10. A study investigator will record the patient's body weight and baseline vital signs. All data will be recorded on data collection sheets, including patients' sex, demographics, medical history, and vital signs, and entered into SPSS (version 24.0; IBM Corp) by the research manager. Confirmation of written consent acquisition for all participants, and statistical analyses will be conducted by the statistician, who will work independently of any data collection.

**Data Analysis:** Data analyses will include frequency distributions and independent-sample t-test to assess differences in pain scores at the various intervals. Mixed-model linear regression will be used to compare changes in pain numeric rating scale across time points. For categorical outcomes (eg, complete resolution of pain), a  $X^2$  or Fisher's exact test will be used to compare outcomes at 60 minutes. Based on the validation of a verbally administered rating scale of acute pain in the ED and the comparison of verbal and visual pain scales, we will use a primary outcome consisting of a minimal clinically meaningful difference of 2 between two groups at the 60-minute pain assessment.

**Sample Size:** Assuming 3.0 SD, alpha of 0.05 and 80% power, we will need 29 patients per group to detect a superiority of AOK with minimal statistically significant difference of 2.0 at 60 min.

**Expected Outcomes:** The primary outcome will include a reduction from baseline of pain scores on numeric rating pain scale (NRS) at 60 minutes. The secondary outcomes will include a need for rescue analgesia and rates of adverse up to 120 minutes.

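### The primary outcome is named as a reduction in NRS but the t-tests are applied to pain scores; no test is labelled primary and no adjustment for baseline NRS is stated

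*Combined protocol and SAP*

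**What the plan says.** The Hypothesis section states: "The primary outcome of this trial is the comparative reduction in participant's pain scores at 60 minutes post-medication administration". Under Study Design, the Expected Outcomes paragraph agrees and adds the reference point: "The primary outcome will include a reduction from baseline of pain scores on numeric rating pain scale (NRS) at 60 minutes".

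The Data Analysis paragraph is worded differently. It describes "a primary outcome consisting of a minimal clinically meaningful difference of 2 between two groups at the 60-minute pain assessment", with no mention of change from baseline. The methods it lists for the pain scale are "frequency distributions and independent-sample t-test to assess differences in pain scores at the various intervals" and a mixed model: "Mixed-model linear regression will be used to compare changes in pain numeric rating scale across time points". Chi-square or Fisher's exact test is reserved for categorical outcomes.

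The Sample Size paragraph reads "Assuming 3.0 SD, alpha of 0.05 and 80% power, we will need 29 patients per group", for a difference of 2.0 at 60 minutes. It does not say whether 3.0 is the SD of the 60-minute score or of the reduction. Baseline NRS is collected under Data Collection Procedures, but no covariate is named for any analysis.

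**The concern.** Three things are left open: whether the tested variable is the 60-minute score or the reduction, which listed method gives the primary result, and whether baseline NRS is used as a covariate. Subtracting baseline is not covariate adjustment. The mixed model might treat baseline as a time point or a covariate, but its terms are not given, and it would not alter a t-test at 60 minutes.

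In any one trial the score and reduction estimates differ by the chance baseline difference between arms, so one t-test can reach significance when the other does not. If the choice is not fixed beforehand, it can be made after the data are seen. With only 58 patients, an unsuitable choice between the two simple tests also loses precision that the baseline measurement could have provided.

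**Working it through.** **Inputs from the plan:** 29 per group, difference 2.0, SD 3.0, alpha 0.05, power 80%.

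**Assumptions, not in the plan:**
- 3.0 is the SD of the 60-minute score.
- Tests are two-sided.
- The baseline SD, sb, is 1.2 to 1.7. A value of 1.7 is what entry scores spread evenly over 5 to 10 would give. The largest possible value, 2.5, needs half the patients at exactly 5 and half at exactly 10, so it is only a theoretical bound.
- The correlation r between baseline and 60-minute NRS is 0.1 to 0.6.

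**Step 1. The plan's own figure.** The exact two-sample t calculation with difference 2.0 and SD 3.0 gives 28.52, so 29 per group, one-sided. Two-sided it gives 36.31, so 37. At 29 per group, power is 80.6% one-sided and 70.4% two-sided. The stated 29 is therefore a one-sided, unadjusted t-test figure. The unstated sidedness is a separate matter.

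**Step 2. SD under each analysis.**
- Raw score: 3.0.
- Change: sqrt(9 + sb² − 6·r·sb).
- ANCOVA: 3·sqrt(1 − r²), with variance multiplied by 1 + 1/(2n − 4) = 1 + 1/54 to allow for chance baseline imbalance.

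Power comes from the non-central t with non-centrality 2/(SD·sqrt(2/29)), with the inflation added for ANCOVA, on 56 df (55 for ANCOVA).

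Example, sb = 1.7 and r = 0.3:
- Raw: 2/(3.0 × 0.2626) = 2.54, power 70.4%.
- Change: SD = sqrt(9 + 2.89 − 3.06) = 2.97; 2/(2.97 × 0.2626) = 2.56, power 71.2%.
- ANCOVA: SD = 3·sqrt(0.91) = 2.86; 2/(2.86 × 0.2626 × sqrt(1.0185)) = 2.64, power 73.6%.

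**Step 3. Power (%), two-sided 0.05, 29 per group.**

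| r | Raw | Change, sb 1.2 | Change, sb 1.7 | ANCOVA |
|---|---|---|---|---|
| 0.1 | 70.4 | 67.0 | 62.2 | 70.0 |
| 0.2 | 70.4 | 70.4 | 66.5 | 71.3 |
| 0.3 | 70.4 | 73.9 | 71.2 | 73.6 |
| 0.4 | 70.4 | 77.7 | 76.4 | 76.9 |
| 0.5 | 70.4 | 81.6 | 81.9 | 81.4 |
| 0.6 | 70.4 | 85.7 | 87.6 | 87.1 |

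- ANCOVA minus raw runs from −0.4 (r = 0.1) to +16.7 (r = 0.6).
- ANCOVA minus change runs from −0.8 (sb 1.2, r = 0.4) to +7.8 (sb 1.7, r = 0.1). At r = 0.4 to 0.6 it lies between −0.8 and +1.4.
- ANCOVA is never more than 0.8 points below the better simple test.
- Change is more precise than raw only if r exceeds sb/6, which is 0.20 at sb 1.2 and 0.28 at sb 1.7. The plan gives neither r nor sb.

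**Step 4. How far the two readings diverge.** The raw and change estimates differ on average by sb·sqrt(2/29)·sqrt(2/π), which is 0.25 NRS points at sb 1.2 and 0.36 at sb 1.7. In simulated bivariate-normal trials with a true difference of 2.0, the two t-tests disagree on significance in about 12 to 16% of trials at sb 1.2 and 16 to 20% at sb 1.7. With no true difference, each test alone holds about 5%. Reporting whichever is significant would give about 6.5 to 7.7%.

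**Step 5. Why ANCOVA removes the ambiguity.** If 60-minute score = a + b·treatment + c·baseline, then score minus baseline = a + b·treatment + (c − 1)·baseline. The residuals and b are unchanged, so the treatment estimate and p-value are the same for both outcomes. The sign flips if the reduction is written as baseline minus score.

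**The case against.** The strongest reply is that the variable is nearly fixed already. Both sentences that define the primary outcome speak of a reduction, and the Data Analysis sentence can be read as giving the clinically meaningful size of a between-group difference in that reduction. The choice of test is narrow too: Fisher and chi-square are for categorical outcomes, the mixed model is for the course over time, and 29 per group is a t-test figure. This stands in part. The text does lean toward reduction, and a reader should not infer two clearly rival endpoints. Yet the t-test is applied to scores, and no sentence ties it to the primary outcome.

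A second reply is that ANCOVA is a preference. Against the change score it gains almost nothing at r = 0.4 to 0.6, and at r = 0.1 it is 0.4 points below the raw t-test. That stands as a limit on the size of the gain. It does not remove the benefit of a single analysis that stays close to the better simple test when r is unknown.

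A third is that "statistical analyses will be conducted by the statistician, who will work independently of any data collection". Independence from data collection does not fix the analysis before the data are seen.

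A reader might infer that the investigators mean to pick the more favourable test. Nothing in the documents indicates this, so the 6.5 to 7.7% error rate is a worst case. A reader might also infer bias or an invalid t-test. Randomization rules that out, because both readings have the same expected difference and each test alone keeps its nominal error rate.

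**Conclusion.** The concern holds as one of precision and pre-specification. The outcome wording and the listed tests need aligning, no analysis is labelled primary, and the collected baseline NRS has no stated role as a covariate.

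Under the stated assumptions, the gain from ANCOVA over the raw score ranges from nil to about 17 power points, depending almost wholly on r. Over the change score it ranges from slightly negative to about 8 points. The open choice matters whatever r is, since the two t-tests disagree in roughly one trial in eight to one in five when the true difference is 2 points.

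Two conditions affect the size:
- With one-sided testing, the only basis on which 29 per group reproduces, raw power is 80.6% and the gain at r = 0.6 is about 12 points.
- If 3.0 is the SD of the reduction instead, the gain over the change score is about 0 to 3 points at sb 1.7 and r = 0.3 to 0.6, before allowing for imbalance.

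Larger gains could be obtained by setting the baseline SD at 2.5, but that describes an implausible entry distribution and should not be used as evidence.

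**What to change.** Use one wording of the primary outcome in the Hypothesis, Data Analysis, Sample Size and Expected Outcomes text, and say which variable the SD of 3.0 describes. Name one primary analysis: ANCOVA of 60-minute NRS on treatment and baseline NRS, reported as the adjusted between-group difference with its confidence interval. Make the mixed model supportive and state how baseline enters it, for example as baseline NRS with categorical time, treatment-by-time and baseline-by-time terms. Make the t-tests at other intervals descriptive.

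The cost is a wording change and one degree of freedom (55 instead of 56), with no new data. The expected power cost is at most about 0.8 points against the better simple test, and about 0.4 points against the raw t-test if r is as low as 0.1.

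### The stated 80% power with 29 per group needs a one-sided 0.05 t-test that the plan never declares; run two-sided, the same unadjusted t-test has about 70% power

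*Combined protocol and SAP*

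**What the plan says.** The Sample Size paragraph under STUDY DESIGN gives the whole calculation in one sentence: "Assuming 3.0 SD, alpha of 0.05 and 80% power, we will need 29 patients per group to detect a superiority of AOK", with a "minimal statistically significant difference of 2.0 at 60 min". It does not say whether alpha is one- or two-sided, and it makes no allowance for dropout.

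The HYPOTHESIS section is directional. It expects that "the administration of AOK will provide better analgesia at 60 minutes post-administration in comparison to OK".

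The Data Analysis paragraph lists two methods for pain scores. One is an "independent-sample t-test to assess differences in pain scores at the various intervals". The other is a regression: "Mixed-model linear regression will be used to compare changes in pain numeric rating scale across time points". Neither is labelled as the primary 60-minute test, and no sidedness is given for either.

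The quantity compared is described in two ways. Data Analysis speaks of a 2-point difference between groups at the 60-minute assessment. HYPOTHESIS and Expected Outcomes speak of a reduction in pain scores. The SD of 3.0 is not attached to either.

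**The concern.** A reader who takes alpha of 0.05 in its usual two-sided sense and applies the planned t-test will not recover 80% power from 29 per group. The shortfall is about ten percentage points, which is too large to be rounding.

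Two things are at stake. First, the power that the trial claims depends on a choice that the plan leaves unstated. Second, the superiority conclusion depends on the same choice whenever the observed difference falls in a certain range. The trial is open-label and this is its primary comparison, so sidedness should not remain open once data are in hand.

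**Working it through.** **Inputs (Sample Size paragraph).** Difference 2.0; SD 3.0; alpha 0.05; power 80%; 29 per group. Equal allocation is implied by the equal group sizes. Dropout is taken as zero because none is stated. Standardised difference d = 2.0/3.0 = 0.667.

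**Step 1: reproduce the plan's figure.** Normal approximation: n per group = 2 × (z₁ + z₂)² / d², with 1/d² = 2.25.
- One-sided 0.05: 2 × 2.25 × (1.645 + 0.842)² = 27.8, so 28.
- Two-sided 0.05: 2 × 2.25 × (1.960 + 0.842)² = 35.3, so 36.

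Exact power from the non-central t distribution, with df = 2n − 2 and non-centrality d × √(n/2):

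| Alpha 0.05 | n = 28 | n = 29 | Smallest n for 80% |
|---|---|---|---|
| One-sided | 79.3% | 80.6% | 29 |
| Two-sided | 68.8% | 70.4% | 37 |

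The plan's 29 is exactly the one-sided t-test answer. For 29 to give 80% two-sided in an unadjusted t-test, the SD would have to be about 2.67 rather than 3.0.

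**Step 2: detectable difference, two-sided, at 29 per group.** The standardised difference giving 80% power is 0.749. Multiplied by 3.0, this is 2.25 points.

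**Step 3: significance thresholds at SD 3.0.** The standard error of the difference is 3.0 × √(2/29) = 0.788, with df = 56.
- One-sided: 1.673 × 0.788 = 1.32 points.
- Two-sided: 2.003 × 0.788 = 1.58 points.
- Observed difference of 2.0: t = 2.0/0.788 = 2.54, two-sided p = 0.014.

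If the true difference is 2.0, the chance of landing between the two thresholds is 0.806 − 0.704 = 0.102, about 10%.

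The thresholds also show that the phrase "minimal statistically significant difference of 2.0 at 60 min" cannot be the decision rule, since significance begins at 1.32 or 1.58.

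**Step 4: would baseline adjustment change this?** The documents give no correlation between the baseline and 60-minute scores, so this step is an assumption throughout. Take 3.0 as the SD of the 60-minute score, residual SD = 3.0 × √(1 − r²), and df = 55. Two-sided power at 29 per group is then:

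| r | 0.2 | 0.3 | 0.4 | 0.5 |
|---|---|---|---|---|
| Power | 72% | 74% | 78% | 82% |

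Power reaches 80% at r of about 0.46. These figures do not apply if 3.0 is the SD of the change.

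**The case against.** The strongest defence is that the one-sided intention is plain enough. The hypothesis is that the combination is better, the trial is sized for superiority of the combination, and the inputs return exactly 29 under a one-sided t-test. Against this stands only a generic phrase about assessing differences, which covers all time points and need not mean a two-sided test. Much of this is right. The two readings are not equally supported, and an undeclared one-sided calculation is the likelier origin of the 29. But a directional hypothesis is often tested two-sided, and it does not by itself set the error rate. If one-sided 0.05 is meant, the reader needs to be told.

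It can also be said that the practical stakes are narrow. This stands. The 1.32 to 1.58 window lies below the plan's own 2-point meaningful difference, and an observed 2.0 is significant under both readings. That limits the severity.

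Three stronger readings are tempting, and the documents do not support them:
- *The sample size is miscalculated.* It is not: the figure is exactly right for a one-sided t-test.
- *Only a one-sided test can reach 80% with 29 per group.* That holds for the unadjusted t-test at SD 3.0. A baseline-adjusted two-sided analysis could reach it if the correlation were high enough. The plan neither makes such an analysis primary nor states a correlation, so this does not support the printed 80%.
- *The t-test and the mixed model are equal candidates for the power basis.* The natural reading is a t-test for the 60-minute contrast and the mixed model for the course over time. What is missing is the label.

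**Conclusion.** The concern holds, and should be fixed. With SD 3.0, a true difference of 2.0 and all 29 patients per group evaluable, the unadjusted t-test has 80.6% power one-sided and 70.4% two-sided at 0.05. The stated 80% therefore rests on a one-sided alpha that the plan implies but never declares. Any loss of patients lowers both figures.

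This goes beyond missing detail, because carrying out the t-test two-sided at the stated alpha would not deliver the stated power. It does not undermine the design: 29 per group can stand, and the formal conclusion turns on sidedness only in the window found above. That window's limits assume an observed SD of 3.0.

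The power figures describe whichever quantity the SD of 3.0 belongs to, the 60-minute score or the change from baseline. The plan does not say which.

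**What to change.** Amend the Data Analysis and Sample Size paragraphs before analysis, leaving 29 per group unchanged.

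1. Name the single primary 60-minute test and its sidedness.
2. Say whether it compares the 60-minute score or the change from baseline, and which of these the SD of 3.0 describes.
3. Make the power statement match the choice:
   - **Two-sided t-test.** Suggested text: *With 29 evaluable patients per group, SD 3.0 and two-sided alpha 0.05, the independent-sample t-test has about 70% power for a difference of 2.0 (80% for 2.25).*
   - **One-sided 0.05.** Declare and justify it for both design and analysis. State that it allows a 5% chance of falsely declaring the combination better, against 2.5% in that direction under a two-sided 0.05 test.
   - **Baseline-adjusted model.** Name it as primary and state the assumed baseline-to-60-minute correlation behind the power figure.

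The cost is a few sentences and no added enrolment. The downside is a less favourable stated power (two-sided), an openly more lenient error rate (one-sided), or a correlation assumption to defend (adjusted model).

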## Adverse Events:

With respect to unique adverse effects of SDK, we will use Side Effect Rating Scale for Dissociative Anesthetics (SERSDA) and Richmond Agitation Sedation Scale (RASS). SERSDA Scale includes fatigue, dizziness, nausea, headache, feeling of unreality, changes in hearing, mood change, general discomfort, and hallucinations with severity of each graded by patients on a five-point scale, with "0" representing the absence of any adverse effects and "4" representing a severely bothersome side effect. RASS evaluates the severity of agitation and/or sedation in accordance to the nine-point scale with scores ranging from "–4" (deeply sedated) to "0" (alert and calm) to "+4" (combative).

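### The only side-effect instruments named target dissociation and sedation, and no procedure is given for eliciting aspirin-type effects, although aspirin is what differs between the arms

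*Combined protocol and SAP*

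**What the plan says.** The Study Objectives section gives efficacy and side effects equal standing: "To compare analgesic efficacy and rates of side effects of a proprietary formulation of orally administered aspirin and ketamine (AOK") is set against oral ketamine alone. Under Study Design, the Design paragraph describes the trial as open-label and as a comparison of efficacy and safety, and it fixes the contrast: "Group I will receive AOK and Group II will receive OK". Both arms contain ketamine; aspirin is the named difference.

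The Expected Outcomes paragraph adds a general safety outcome: "The secondary outcomes will include a need for rescue analgesia and rates of adverse up to 120 minutes". It does not say which events count or how they are found.

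The Adverse Events section is the only place where a collection tool is named: "With respect to unique adverse effects of SDK, we will use Side Effect Rating Scale for Dissociative Anesthetics (SERSDA"), together with the RASS. SDK is not defined and is not the name of either arm. The SERSDA items are "fatigue, dizziness, nausea, headache, feeling of unreality, changes in hearing, mood change, general discomfort, and hallucinations", each graded by the patient from 0 to 4. For the second scale the text says "RASS evaluates the severity of agitation and/or sedation". No assessment times are given for either scale.

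The Exclusion Criteria paragraph shows that aspirin risk was considered at entry. It lists "active PUD, history of GI Hemorrhage", and also aspirin allergy, recent aspirin or NSAID use, and renal or hepatic insufficiency.

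**The concern.** A comparison of side-effect rates should be able to see the effects of whatever differs between the arms. Here the named instruments are aimed at the component the arms have in common. Effects that aspirin could add are left to items that happen to overlap, or to whatever patients mention unprompted.

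Two things are at stake. First, an effect that is never asked about cannot be recovered at analysis. Second, patients and staff know who received aspirin, so unprompted reports may be more readily offered or noted in one arm than the other. Similar SERSDA and RASS results could then be presented as similar overall safety, which those scales cannot support. The primary pain outcome is not affected.

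**Working it through.** **1. The plan's own figure.** The Sample Size paragraph gives 29 per group from SD 3.0, difference 2.0, alpha 0.05 and 80% power. By the normal approximation, n = 2(z_alpha + z_beta)² × SD²/difference².

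- One-sided: 2 × (1.645 + 0.842)² × 9/4 = 27.8, so 28. The t-test version gives 28.5, so 29.
- Two-sided: 2 × (1.960 + 0.842)² × 9/4 = 35.3, so 36. The t-test version gives 36.3, so 37.

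The stated 29 therefore reproduces with a one-sided alpha of 0.05; the plan does not state sidedness. That is a separate matter. Only the 29 is used below.

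**2. Coverage of aspirin-type effects.** SDK is taken here to refer to ketamine, since both scales concern dissociation or sedation.

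| Effect | SERSDA item | RASS |
|---|---|---|
| Nausea | yes | no |
| Hearing change | yes | no |
| Epigastric pain or heartburn | none specific; general discomfort might register it | no |
| Vomiting | none | no |
| Bleeding | none | no |
| Hypersensitivity (rash, wheeze) | none | no |

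Three of the nine SERSDA items (nausea, general discomfort, changes in hearing) could move with an aspirin effect, but they would not identify it.

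**3. Other routes for collection.** Three places might supply one.

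- Expected Outcomes names a general adverse rate but no method.
- Eligibility Criteria requires that patients can describe unwanted effects. That is a condition of entry, not a collection step.
- Data Collection Procedures lists some data-sheet contents. The list is open-ended and has no adverse-event field. It also omits post-dose pain scores and rescue analgesia, which are plainly planned, so it settles nothing either way.

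**4. What 29 patients could show if asked.** The documents give no rates for aspirin-type effects, so the rates p are assumed. Expected events = 29p; chance of at least one = 1 − (1 − p)^29.

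| Assumed p | Expected events in 29 | Chance of at least one |
|---|---|---|
| 2% | 0.6 | 44% |
| 5% | 1.5 | 77% |
| 10% | 2.9 | 95% |
| 20% | 5.8 | over 99% |

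If the question is asked and 0 of 29 report the effect, the one-sided 95% upper bound is 1 − 0.05^(1/29) = 9.8%. The upper limit of a two-sided 95% exact interval is 1 − 0.025^(1/29) = 11.9%.

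**5. Power to compare arms.** This is for Fisher's exact test, two-sided 5%, 29 per group, summing binomial probabilities over all significant tables. Power is about 9% for 15% versus 5%, 22% for 20% versus 5%, and 61% for 30% versus 5% (all rates assumed).

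**The case against.** The strongest reply is that the Adverse Events sentence is limited to the effects peculiar to one drug and does not claim to describe all adverse-event capture. Read with the general adverse rate to 120 minutes, and with the requirement that patients can describe any effect, it leaves room for other events to be recorded. This stands in part. A reader might infer that the plan measures side effects solely with these two scales, or that the data sheet has no place for anything else. The documents do not support either inference; they are silent on how other effects are elicited.

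A reader might also infer that the trial could say nothing about aspirin effects. That goes too far as well, because nausea, general discomfort and hearing change could show a difference between arms.

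Nor are the scales misplaced. Whether adding aspirin alters dissociative or sedative effects is a fair question. The reviewed text gives no doses and describes both products as proprietary formulations, so equal ketamine exposure cannot be assumed.

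Finally, with 29 per group, entry exclusions aimed at gastrointestinal and renal risk, and observation to only 120 minutes, few events are likely and a formal comparison would be weak. That is right, and it limits what the added items can prove. It does not justify leaving the effects unasked when comparing side effects is an objective.

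**Conclusion.** The concern holds as a gap in measurement. The only named instruments are directed at the shared component, no item covers epigastric pain or heartburn, vomiting, bleeding or hypersensitivity, and no procedure for eliciting other effects is stated. The likely result is under-capture of aspirin-type effects and, because the trial is open-label, possible reporting differences between arms. The documents do not show that such effects would go unrecorded altogether.

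The size is modest: roughly 0.6 to 6 events per 29 patients at assumed true rates of 2% to 20%, and a 9.8% one-sided upper bound if none is seen. The change should be made because it is cheap and serves a stated objective, but it does not bear on the primary analysis. The conclusion rests on SDK referring to ketamine and on there being no adverse-event procedure outside the reviewed text.

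**What to change.** In the Adverse Events section, state how all adverse effects are elicited in both arms:

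- Name the assessment times up to 120 minutes, for SERSDA and RASS as well as for the additions.
- At each time, ask one open question about any unwanted effect, then a short yes/no list with identical wording in both arms: epigastric pain or heartburn, vomiting, bleeding, rash or wheeze.
- Report counts by arm over the full 120 minutes with exact confidence intervals, next to the SERSDA and RASS results. The categorical test in Data Analysis is tied to 60 minutes, so the window for adverse effects needs its own sentence.
- Define SDK.

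If the items are not added, limit the safety conclusion to the effects that SERSDA and RASS measure.

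The cost is a few lines on the data sheet and slightly more data collection per patient; the sample size does not change. The downside is that the counts will be low and mainly descriptive, and structured questions reduce, but do not remove, the effect of open-label knowledge on what patients report.

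### No pre-dose SERSDA score is planned and no rule separates arrival symptoms from new ones, so the comparison of side-effect rates can be diluted toward no difference

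*Combined protocol and SAP*

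**What the plan says.** Study Objectives names the comparison of side-effect rates alongside analgesic efficacy. Expected Outcomes makes "rates of adverse up to 120 minutes" a secondary outcome.

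Data Collection Procedures lists what is taken at baseline: the NRS pain score, then "A study investigator will record the patient's body weight and baseline vital signs", plus sex, demographics and medical history. SERSDA and RASS are not on that list.

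The Adverse Events section names the two scales. SERSDA has nine items, with the "severity of each graded by patients on a five-point scale" running from 0 (no adverse effect) to 4 (severely bothersome). The section gives no assessment time for either scale, before or after dosing. It states no cut-off that turns a grade into an adverse event and no rule for symptoms that precede the drug. Data Analysis does not mention the scale scores.

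On entry, the Subjects and Eligibility Criteria paragraphs call for acute musculoskeletal pain, traumatic or not, scoring at least 5 (Subjects), in patients who are awake, alert and oriented.

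**The concern.** Pain is analysed as a reduction from each patient's own baseline. Side effects have no planned baseline. Several SERSDA items are non-specific: a patient in acute pain may well arrive tired, nauseated, dizzy or with a headache, and general discomfort is close to the entry condition itself. If such a symptom is still present after dosing and is tabulated, it enters the arm's side-effect rate although the drug did not cause it.

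Two things are at stake. First, background symptoms raise the rate in both arms and compress the difference between them. Second, with 29 patients per arm the groups may differ by chance in arrival symptoms, and without a pre-dose score nobody can see or adjust for that. A baseline not taken before dosing cannot be recovered at analysis.

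**Working it through.** **The plan's own figure.** The only sample size given is for pain: "we will need 29 patients per group", from "Assuming 3.0 SD", "alpha of 0.05 and 80% power" and a "minimal statistically significant difference of 2.0 at 60 min". The normal formula is n = 2·SD²·(z_α + z_power)²/δ².

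- One-sided: 2 × 9 × (1.645 + 0.842)²/4 = 27.8, so 28. With the t distribution it is 28.5, so 29.
- Two-sided: 2 × 9 × (1.960 + 0.842)²/4 = 35.3, so 36. With the t distribution it is 37.

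The stated 29 is therefore a one-sided result, which fits the directional wording "to detect a superiority of AOK". It has no bearing on this point beyond fixing the arm size. No figure is given for side-effect rates, background prevalence or power on side effects.

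**Dilution of a rate difference.** Let p0 be the share of patients who have a symptom on arrival and still report it after dosing. Take p0 as equal in both arms and independent of the drug effect, and let p be the drug-caused rate. If persisting symptoms are counted:

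observed rate = p0 + (1 − p0)·p

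observed difference = (1 − p0)·(p_AOK − p_OK)

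All values of p0 and p below are assumptions. Power is for 29 per arm, two-sided 0.05, normal approximation.

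| True rates | p0 | Observed rates | Difference | Power |
|---|---|---|---|---|
| 40% vs 30% | 0 | 40% vs 30% | 10 points | 0.12 |
| 40% vs 30% | 30% | 0.30 + 0.70×0.40 = 58% vs 0.30 + 0.70×0.30 = 51% | 7 points | 0.08 |
| 40% vs 30% | 50% | 0.50 + 0.50×0.40 = 70% vs 0.50 + 0.50×0.30 = 65% | 5 points | 0.06 |
| 50% vs 30% | 0 | 50% vs 30% | 20 points | 0.34 |
| 50% vs 30% | 10% | 55% vs 37% | 18 points | 0.28 |
| 50% vs 30% | 30% | 65% vs 51% | 14 points | 0.19 |
| 50% vs 30% | 50% | 75% vs 65% | 10 points | 0.13 |

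If the true difference is zero, it stays zero in expectation.

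**Chance imbalance.** Take two independent binomial counts with n = 29 and an assumed arrival prevalence of 30%. The standard error of the difference is √(2 × 0.3 × 0.7/29) = 0.12. The exact probability that the arms differ before dosing by at least 3 patients (3/29 = 10.3 points) is 0.47. For at least 6 patients (20.7 points) it is 0.11.

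**Mean severity instead of rates.** An equal additive background cancels in a difference of mean grades, apart from ceiling effects and added variance. The dilution therefore belongs to rates, which are what the plan names.

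**The case against.** The best defence is that the plan is silent rather than wrong. No SERSDA schedule is given at all, so the absence of a pre-dose score is inferred from the baseline list and not stated as a decision. That is fair, and it widens the gap: post-dose times are missing too.

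A reader might infer that every grade above 0 counts as an adverse event, and hence that most patients in both arms will be positive on at least one of nine items. The text does not say so. It describes the anchors at 0 and 4 and sets neither a cut-off nor an any-item composite. The anchors also ask about side effects rather than symptoms, and patients must be able to describe adverse effects they experience, so some will leave out what they arrived with. Patient attribution is imperfect protection, particularly in an open-label trial, but it is some.

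For RASS the concern is weak. Entry requires alert, oriented patients and excludes altered mental status, so baseline sedation is largely ruled out. Mild agitation from pain remains possible.

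The practical effect is also limited by the trial's size. At 40% vs 30%, the 95% interval for the difference has a half-width of about 1.96 × √(0.4×0.6/29 + 0.3×0.7/29) = 24 points, so a 3-point shift changes little of what the trial can conclude. This stands, and it keeps the point modest. It is not a reason to skip a baseline that costs almost nothing.

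**Conclusion.** The point holds as a cheap improvement to a secondary outcome. SERSDA is absent from the baseline list, no assessment times are given, and no rule separates pre-existing from new symptoms. If arrival symptoms persist and are tabulated, both arms' rates rise and a true rate difference shrinks by the factor (1 − p0): 10 points become 7 at an assumed 30% and 5 at an assumed 50%. This rests on a non-zero background, a non-zero true difference, a rate-type analysis and equal persistence in the two arms. The documents do not allow its size to be estimated.

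A reader might infer that the missing baseline biases the comparison in favour of AOK. It does not do so systematically. Randomisation balances arrival symptoms in expectation, so the effect is dilution toward no difference, whichever arm has the higher rate. Chance imbalance can go either way. The significance test allows for it, but without a pre-dose score it cannot be adjusted for or told apart from a drug effect in the data obtained. The primary pain outcome is unaffected.

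**What to change.** 1. Record SERSDA before dosing, together with the baseline NRS. Add RASS at the same time, as a lesser matter.
2. State the post-dose assessment times for both scales, up to 120 minutes.
3. Define an item as an adverse effect only if its post-dose grade is new or worse than the patient's own pre-dose grade. Report the grade distribution per item and by arm, before and after dosing, beside the rates.

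The cost is a few minutes per patient at enrolment, an extra row on the data sheet and a sentence or two in Data Analysis. No patients or staff are added.

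The rule has limits. A pre-dose grade of 4 cannot worsen. Comparing the worst of several post-dose ratings with a single baseline rating overstates worsening in both arms, so rates at each stated time should be shown too. The rule removes the background from the rates, but restores the full difference only if a drug effect in someone already symptomatic shows as a higher grade. With 40% vs 30% and p0 = 30%, if no such patient is ever graded worse, the rates are 0.70×0.40 = 28% and 0.70×0.30 = 21%. That is still 7 points, although the ratio 28/21 = 1.33 matches 40/30, whereas 58/51 = 1.14 does not. With no placebo arm, neither arm's rate becomes a pure drug rate; what improves is the comparison between arms.
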